6.4 Stage One Procedure – Group A

(Please see prosthetists pathway diagram on Page 13)

Prosthetists will be informed of the study via the study's clinic leads [name] – Bristol NHS Opcare prosthetics services clinic, and [name] – Cambridge and Norwich NHS Opcare prosthetics services clinics. The study will be discussed at team meetings. A PIS and invitation letter will be circulated to all interested prosthetists via email. Prosthetists who would like to take part will have an opportunity to ask questions and will then be asked to complete a consent form by a member of the Clinical Investigation team. They will be able to consent for both Stages, or just Stage One, or just Stage Two. This is set out clearly in the PIS.

NHS

Once recruited, the participating prosthetists will be invited to attend an in-person training session at their clinic carried out by the study researchers to introduce them to the ATFS and guide them through an example case. The objective of the training session will be to ensure they feel comfortable to use the software as an aid in designing a socket for a patient. They will also receive a printed and electronic 'Quick Reference Guide' and be shown the in-software information videos. Next, the prosthetist will attend the assessment appointment of an eligible patient. During the assessment appointment, after providing the patient with the study invitation letter and the PIS, the prosthetist will capture the patient's residual limb shape with direct a 3D scan of the limb or scanned plaster cast of the limb, and other measurements, as is normal clinical practice. At the end of the assessment appointment, if the patient would like to participate then the attending prosthetist, site Principal Investigator or an attending study researcher will receive their consent.

The prosthetist will then access the ATFS, via a web-browser, using login details provided by the study researcher. The prosthetist will upload the limb shape file and use the ATFS to support them designing a socket for their patient. They will be asked to think aloud while using the ATFS. They will be recorded as they use the software, and the study researcher will be available to help where required. Recording will be via screen-capture with audio.

They will then send the designed socket file to their workshop or central fabrication facility for manufacture into a socket as per their clinic's normal process.

As per normal care, once the socket has been made the prosthetist will carry out a fitting appointment for the patient, taking and recording standard outcome measures (e.g. socket comfort score, Key Performance Indicators (KPIs) for their clinic). They will discuss the socket fit with the patient and make minor or major socket adjustments as required, using the ATFS software where digital adjustments are needed, leading to delivering the definitive socket for the patient. The study researcher will be on-call to help where required with use of the ATFS. The socket comfort score will be collected from the prosthetist by a study researcher.

The study researcher will arrange to conduct a 30-minute semi-structured interview with the prosthetist after delivery of the definitive socket to the patient, about their experience creating a socket with the aid of the ATFS. Physical adjustments carried out on the socket during fitting appointments will also be captured during the interview. The prosthetist will have the choice of an in-person, virtual (via MS Teams video call software), or telephone interview. The interview will be arranged flexibly around the prosthetist's schedule.

Training materials on using the ATFS will also be evaluated through the semi-structured interview.

For the iterative development of the software being carried out during this first stage, the prosthetist may be asked to carry out stage one of the study at least once more. Software updates will be pushed throughout Stage One while developing the ATFS and researchers will be present to support ATFS use and provide training as required. The Stage One endpoint and number of usability iterations required in Stage One will be determined by the technology development process (e.g., feature freeze), and the participating clinicians being comfortable to use the ATFS throughout the full socket design process independently without resorting to current socket design process (i.e. no further observation or detection of a usability problem with final ATFS version reached and ready for summative testing).

283-04A-04 (XF) Study Protocol IRAS ID: 317901 HRA REC REF: 24/LO/0126 12 ERGO NO: 81419

See Group B – Stage 1 semi-structured interview format in the Appendices of this document in Section 16.1.

Stage One Group A (participating prosthetists) Pathway Diagram:

Stage One (Formative) testing - 081222

283-04A-04_(XF)_Study Protocol

6.5 Stage Two Procedure – Group A

Stage Two consists of Summative usability testing of the fully developed ATFS. Training will be provided if a participant interested in taking part in only Stage Two did not attend a Stage One training session.

NHS

North Bristol

(Please see prosthetists pathway diagram on Page 15)

Identical to Stage One except for the following changes:

- i. The prosthetist will use the ATFS independently while being recorded but without thinking aloud.
- ii. No changes will be made to the ATFS during this stage.
- iii. The study researcher will arrange to conduct a 30-minute semi-structured interview with the prosthetist after delivery of the definitive socket to the patient, about their experience independently creating a socket with the aid of the ATFS, plus their views on comparisons against their standard CAD/CAM design workflow.

The interviews will be arranged flexibly around the prosthetist's schedule.

See Group A – Stage 2 semi-structured interview schedule in the Appendices of this document in Section 16.1.

NHS Cambridge **University Hospitals**

NHS

Stage Two Group A (participating prosthetists) Diagram:

Stage Two (Summative) testing - 081222

CONFIDENTIAL THIS DOCUMENT IS PROPRIETARY INFORMATION AND IS NOT TO BE REPRODUCED OR DISCLOSED WITHOUT PRIOR WRITTEN APPROVAL

6.6 Stage One and Stage Two Procedure – Group B

Group B – Adults with limb loss

Their involvement in this study will form part of a patient's usual care which will be provided according to the NHS Trust's most up-to-date infection prevention and control guidance. When a person with a transtibial amputation who meets the inclusion criteria is referred for prosthetic limb fitting at one of the three participating NHS prosthetics centres, or contacts one of the three centres for an assessment appointment. For both Stages of the study, an invitation letter and Participant Information Sheet (PIS) will be sent from participating clinics to potential participants ahead of their assessment appointment to allow them sufficient time to consider taking part in the study prior to the appointment. The PIS will provide them with information about the study and invite them to consider taking part. They will have sufficient time to read it prior to being asked to give informed consent. The patients will have as long as they feel necessary up to the end of their assessment appointment to decide whether they would like to take part and have their sockets designed with the aid of the ATFS. During their assessment appointment, they will have an opportunity to ask questions about the study to their prosthetist, and if they are happy and meet all the eligibility criteria they will be asked to read and sign a consent form. If they do not wish to take part in the study, they will continue to receive the usual care at their prosthetics centre and will be informed about this in the PIS.

At their assessment appointment, the prosthetist will take a scan of the participant's limb using a 3D scanner as per normal care. The rectification and design process was described within the prosthetists' (Group A) procedures (sections 5.4 and 5.5).

At the fitting appointment, the participant will try on their socket as per normal care with the prosthetist evaluating standard outcome measures, discussing the socket fit with the participant, and making adjustments to the socket as required. During trialling, the standard outcome measures (e.g. socket comfort scores and Key Performance Indicators (KPIs) for their clinical service) will be taken by the prosthetist. After both participant and the prosthetist are happy, the participant will take their new socket home.

This procedure matches normal care except that the socket will have been designed with the aid of the ATFS rather than the standard CAD/CAM socket design process for the clinic.

6.7 Follow-up Care

Follow-up care for participating patients to address any concerns following their fit/delivery appointment will be through existing normal standard of care pathways, i.e., planned review appointments or the patients contacting the clinic directly.

6.8 End of Study Stage One end point

283-04A-04_(XF)_Study Protocol

IRAS ID: 317901 ERGO NO: 81419 HRA REC REF: 24/LO/0126 16

NHS North Bristol NHS Trust

Once the final ATFS version has been reached ready for summative testing. The number of iterations required in Stage One will be determined by the technology development process (e.g., feature freeze), and the participating clinicians being comfortable to use the ATFS throughout the full socket design process independently without resorting to their current socket design process (i.e., no further observation or detection of a usability problem).

Stage Two end point

Once the ATFS has been used to support the socket design for 19 participating patients across the three sites.

7. Data analysis

Continuous data (i.e. time taken for initial rectification and socket design using the ATFS) will be summarised using mean, standard deviation, median and 25th and 75th percentiles; categorical data (i.e. socket comfort scores) will be summarised using number of events and percentages. Completion rates of the data above will be tracked.

The qualitative data collected from audio recordings will be transcribed verbatim by a University of Southampton approved subcontractor, with whom the University has a written agreement of confidentiality. A second researcher will check a sample of data transcripts against the screen capture with audio and interview recordings for accuracy, and will interrogate the validity of the coding against the raw data. The verbal content of the interviews, and the verbal and observational data of the screen capture recordings will be analysed. The data will be fully anonymised to remove any identifying (i.e., names) and confidential information. Interview data for Stage 1 and 2 will be analysed separately using thematic analysis; a flexible approach will be applied to systematically group and identify meaning within the data^{13, 14}, and will be useful for the more in-depth discussions within the interviews. This analytical approach will consist of a series of steps including: familiarisation with the data, a combination of hand-coding and the QSR International NVivo 11 software (http://www.qsrinternational.com/what-is-nvivo), and searching, defining and reviewing themes.

8. Adverse events and Serious Adverse Events Reporting

NHS

In accordance with MEDDEV 2.7/3 all serious adverse events (SAEs) will be fully recorded, and the competent authority in which the clinical investigation is being performed (the MHRA) will be notified by the sponsor of the clinical investigation (Radii Devices Ltd) immediately, but not later than two calendar days after awareness by the sponsor of the SAE or of new information in relation with an already reported event.

The Principal Investigator or clinic lead at participating sites will inform the sponsor of SAEs immediately, but not later than three calendar days after their awareness of the event.

Serious adverse events would be regarded as an event occurring during participation (for example an injurious fall) that:

- Leads to death or injury leading to permanent impairment to a body structure or body function.
- Leads to a serious deterioration in health of the participant that either results in:
 - A life-threatening illness or injury, or
 - A permanent impairment of a body structure or a body function, or
 - In-patient hospitalization or prolongation of existing hospitalization, or 0
 - In medical or surgical intervention to prevent life threatening illness 0

Non-serious adverse events would be regarded as an event occurring during participation reported by the patient as in their usual clinical care pathway:

> Any untoward medical occurrence (for example a socket material failure), unintended disease or injury

The trial design minimises risk as participants are following their usual care pathway for receiving a new prosthetic socket. AEs related to socket use will be naturally collected, recorded, and managed by the prosthetists as part of the usual care procedures.

A causality assessment of the relationship between the use of the medical device and any occurrence of SAEs will be carried out by the sponsor in collaboration with the clinical judgement of the Principal Investigator and clinic leads, and using relevant documents such as the investigator's brochure, the clinical investigation plan, protocol, risk analysis and device details.

For the purpose of harmonising, reporting of SAE's will be categorised according to five different levels of causality as defined in MEDDEV 2.7/3:

- Not related
- Unlikely
- Possible
- Probable
- Causal relationship

Cambridge University Hospitals

This clinical investigation minimises the risk of SAEs with a causal relationship as the standard clinical care pathway is being followed so procedures (design and fitting of a prosthetic socket) would still have been applied to the patients in the absence of the ATFS use.

NHS

North Bristol

9. Ethical considerations and risks

Informed consent

Written informed consent will be received from all participants prior to entry to Stage One and Stage Two of the study.

For Group A participants, the consenting process will be conducted by a member of the study research team at their respective NHS site.

For Group B participants, the consenting process will be conducted by a member of the patient's usual multidisciplinary team (MDT) (e.g. their prosthetist or the site Principal Investigator) or by one of the study research team in attendance in their normal clinical care setting, according to Good Clinical Practice (GCP) guidelines.

All prospective participants will be provided with a detailed PIS and provided the opportunity to ask any questions regarding the study. We will also emphasise that participants are free to withdraw from the study at any time without any explanation, and that doing so will not affect their treatment or care or employment in any way. Patient participants' involvement in the study will be documented in their medical record by site Principal Investigators uploading completed consent forms.

Anonymity

All participants will be allocated a study ID when recruited. This ID will be used during analysis and dissemination of the research (via journal publications or presentations) to ensure data remains anonymous.

Right to withdraw

Participants in both groups have the right to withdraw from any aspect of the study and at any time during the study without giving a reason, or any of their legal, clinical or employment rights affected. This information will be included in the PIS and consent form, and the participants will be advised of it verbally throughout the process of the study.

Data security

The research team at Cambridge University Hospitals NHS Foundation Trust, Norfolk Community Health and Care NHS Trust, North Bristol NHS Trust, University of Southampton and Radii Devices will comply will all aspects of the UK General Data Protection Regulation (UK GDPR).

Encrypted recording devices will be used as prosthetist participants use the ATFS Software, when thinking aloud, and during the interviews. Recordings will be anonymised at-source and file-naming. A transcription service officially approved by the University of Southampton (collaborating on this study) will transcribe the recordings. There is a written agreement of confidentiality (SLA) between the transcription service provider and the University of Southampton. Once transcribed, recordings

North Bristol NHS Trust

will be deleted from the recording device. The transcription data will be transferred to the study team via a secure, password-protected system.

All information collected during the course of the study will be kept strictly confidential. Information will be held securely on paper and electronically at Radii Devices Ltd, including appropriate storage, restricted access, on password protected Radii Devices machines, and disposal arrangements of patients' identifiable details on their consent form. Participants will not be identified in the results of the study. Data will be archived for a minimum period of 10 years following the end of the study. Personal data will be processed according to GDPR.

Personal Protective Equipment (PPE) considerations

PPE will be used according to each trust's Infection Prevention and Control guidelines. As the study will be integrated with usual care, PPE will be worn as per usual care. On site research activities will be undertaken by the attending study researcher and the clinical teams who usually work at each prosthetics centre and are familiar with Trust PPE guidance.

10. Study Management & Monitoring

This study will be overseen by a Chief Investigator and the study Principal Investigators at each participating site and managed by the study team members, with periodic clinical investigation meetings, as designated within the roles and responsibilities section 1.4 of 283-04A-01 (XE) Clinical Investigation Plan. Briefly, approximately weekly technical and onsite investigator meetings, and once every two month clinical investigation and grant study meetings will be held for updates and monitoring of documentation on recruitment progress, practical issues and challenges, study data and adverse events reporting, etc., to ensure effective collaborative communication and efficient progress.

For each Group B (patient) participant a study researcher will complete an E-Case Report Form (E-CRF, see Section 16.2) to check off that study activities have been carried out and that screen recording and semi-structured interview audio recordings have been saved in the master site file.

The monitoring plan can be observed within Section 12.6 of 283-04A-01 (XE) Clinical Investigation Plan. Briefly, there will be one monitoring visit at each participating site during Stage Two. A single monitoring visit at each study site was determined appropriate taking into account the low complexity and risk and minimal deviation from current clinical processes associated with this clinical investigation. Carrying out the monitoring visit at each site nearer the end of Stage Two will be carried out so that the monitor is able to verify all of the necessary consent forms and e-CRF forms.

At each monitoring visit, the monitor will have a briefing meeting (approximately one hour) with the site Principal Investigator and on-site investigators ahead of verifying consent forms and E-CRF forms as specified in Section 12.6 of 283-04A-01 (XE) Clinical Investigation Plan.

NHS Trust

Schedule Of Events (SoE) 11.

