Since 2014, understanding how best-practice in engineering design can support prosthetic socket fitting has been a key focus of University of Southampton researchers. This research has resulted in the spin out of a company (Radii Devices Ltd.) and the development of technology to meet the patient and clinic need, guided by input from prosthetics service providers including Opcare (Ability Matters Group Ltd.), and patients. This study is assessing the usability of the developed software, Adaptive Templates Fitting System (ATFS), incorporating the technology. These Adaptive Templates use existing socket fitting data, which is analysed to link rectification approaches to particular patient characteristics. The data includes socket designs, limb shapes, and outcome measures from previous socket fittings in the NHS. The ATFS is derived from these datasets in two ways:

1) Extracting features from the complex 3D shapes of the residual limb and prosthetic socket, used for past patients. These may include individual rectifications, and clinically relevant residual limb features, such as the length, and how bulbous or conical their limb is.

2) Making a recommendation to a prosthetist for socket rectifications, using a probabilistic approach which considers the likelihood of particular socket design strategy working for a new patient's characteristics.

Unlocking the potential of data to support fitting will assist more efficient learning and design, potentially leading to:

- Reducing time to fit (fewer iterations, reduced waiting time and, eventually, reduced appointment backlog)
- Reducing rejection rates (improved comfort and functional stability)

NHS

North Bristol

• Improving patient outcomes, participation and quality of life (reduced incidence of soft tissue problems, from irritation and sores to major injuries such as pressure ulcers; reduced incidence and progression of comorbidities, including sequelae of immobility, obesity, vascular disease and mental health impacts)

The developed technology, using computational geometry, data science and biomechanical engineering expertise to extract meaningful data about the rectification process has been applied to below-knee prosthetic socket design data provided by Opcare. This data helped form an initial demonstration of the feasibility of linking rectification approaches to particular patient characteristics and objectively analysing personalised design approaches by expert prosthetists⁶.

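### The SAE list's intervention criterion is narrower than the outcomes listed beside it, so a serious injury averted without admission is classed as non-serious

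*Protocol*

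**What the plan says.** Section 8 of the Protocol (Adverse events and Serious Adverse Events Reporting) defines an SAE at two levels.

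The first level is an event that "Leads to death or injury leading to permanent impairment to a body structure or body function".

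The second level is a serious deterioration in health that results in one of four things, labelled (a) to (d) here for reference:

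- (a) "A life-threatening illness or injury, or"
- (b) "A permanent impairment of a body structure or a body function, or"
- (c) "In-patient hospitalization or prolongation of existing hospitalization, or"
- (d) "In medical or surgical intervention to prevent life threatening illness"

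Non-serious adverse events are any other untoward medical occurrence, disease or injury, described as "an event occurring during participation reported by the patient as in their usual clinical care pathway". The section adds that prosthetists collect, record and manage socket-related adverse events within usual care.

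Three duties are stated only for SAEs: notice from site to sponsor within three calendar days, notice from sponsor to MHRA within two calendar days, and causality grading on five levels.

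**The concern.** Criteria (a) and (b) set out what the protocol regards as a serious outcome. Criterion (d) covers treatment that stops a serious outcome from happening, so it would be expected to cover the same outcomes. It names only life-threatening illness. Life-threatening injury, which is in (a), and permanent impairment, which is in (b), are missing.

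The omission matters here because the harms the protocol mentions are largely injuries. Section 8 gives an injurious fall as its example of an SAE. Section 4, listing what better fitting might achieve, mentions "reduced incidence of soft tissue problems, from irritation and sores to major injuries such as pressure ulcers". On the protocol's own account, tissue injury is a foreseeable consequence of a poor socket. Section 4.1 makes patient safety part of the study objective.

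What is at stake is the handling of individual events. An event classed as non-serious has no stated deadline for reaching the sponsor or MHRA and no stated causality assessment.

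**Working it through.** No sample size, rate or error level enters this point, so there is nothing to compute. The check applies the Section 8 list to cases.

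**Step 1: compare the criteria.**

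| Outcome | Serious if it occurs? | Serious if treatment averts it, under (d)? |
|---|---|---|
| Life-threatening illness | Yes, (a) | Yes |
| Life-threatening injury | Yes, (a) | Not named |
| Permanent impairment | Yes, (b) and the first level | Not named |

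**Step 2: apply the list.** In each case the patient has an injury that causes a serious deterioration in health and is treated to avert a worse outcome.

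| Case | Criterion met | Class |
|---|---|---|
| 1. Permanent impairment occurs despite treatment | (b) | SAE |
| 2. Impairment averted, with in-patient stay or prolonged stay | (c) | SAE |
| 3. Impairment averted by out-patient or day-case treatment, not life-threatening | None | Non-serious |
| 4. Life-threatening injury averted by out-patient treatment | None, since (d) names illness only | Non-serious |

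The gap is cases 3 and 4. Cases 1 and 2 are captured as the text stands.

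**Step 3: what cases 3 and 4 lose.** They remain adverse events, recorded by the prosthetist. Section 10 says adverse event reporting is followed at periodic study meetings. What they lose is the two timed notices and the causality grading. The fallback is not strong on the face of this document: none of the twelve items of the E-CRF in Section 16.2 is an adverse event field, and Section 10 summarises the monitoring visit as verifying consent forms and E-CRFs. Both sections point to the Clinical Investigation Plan, which may provide more.

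**Step 4: repeat with the criterion widened to the outcomes in (a) and (b).** Cases 3 and 4 become SAEs under (d), and cases 1 and 2 do not change. Minor irritation stays non-serious, because all four criteria still require a serious deterioration in health.

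**The case against.** **The hospitalisation criterion already covers much of this.** This stands, and it limits the point. A reader might infer that any treatment given to save an injured limb falls outside the SAE definition. The document does not support that: admission or a prolonged stay makes the event an SAE whatever the treatment was meant to prevent.

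**The remaining events are not lost.** This also stands. A reader might infer that they go unreported. They are still adverse events under Section 8, recorded by prosthetists and open to discussion at study meetings. They escape expedited reporting and causality grading only.

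**The frequency is unknown.** Correct. The protocol does not say how often a socket injury needs intervention, or how often that is done without admission. Calling this the likeliest serious harm would go beyond the text. So would turning one hypothetical event into a percentage of the planned sample: the recruitment total is an upper limit, and no SAE proportion is planned as an outcome. Section 4.1 lists comfort scores and design time as the measures for verifying safety and efficiency.

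**Prosthetist-observed sores.** The phrase about events reported by the patient might suggest that a sore seen only by the prosthetist is not an adverse event. The later sentence, that prosthetists collect and record socket-related events, largely answers this. The two statements could be reconciled, but no gap in collection is shown.

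**The text may be incomplete, or fuller elsewhere.** The copy examined has stray characters around the last two sub-items, and the final one has no full stop, so lost words cannot be excluded. The stray characters look like displaced bullet marks, however, and the criterion reads as a complete phrase. The Clinical Investigation Plan and MEDDEV 2.7/3 are cited but not available here, so no comparison with them is made. Even if they are fuller, the protocol should agree with them.

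**Conclusion.** The point holds in a limited form. Criterion (d) in Section 8 does not match the outcomes that the same list treats as serious. A serious deterioration treated without in-patient admission is classed as non-serious when the treatment averts permanent impairment or a life-threatening injury. It therefore has no stated three-day notice to the sponsor, two-day notice to MHRA or causality grading.

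The size is two of the four cases examined, with no estimable frequency. This is a defect in a reporting definition. It does not show that the study's safety conclusion would be wrong.

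The conclusion assumes that the printed criterion is complete, that sites apply it as worded, and that no fuller definition in the Clinical Investigation Plan overrides it. Correction is still worthwhile, because verifying safety is a stated purpose of the study and the change is small.

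**What to change.** In Section 8, widen the last SAE criterion to the outcomes already listed above it: medical or surgical intervention to prevent (i) life-threatening illness, (ii) life-threatening injury, or (iii) permanent impairment of a body structure or function. First confirm the printed wording in the PDF. Then check that the revised text agrees with the Clinical Investigation Plan and with MEDDEV 2.7/3.

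At most, in the same edit, reconcile the phrase about events reported by the patient with the later sentence that prosthetists collect and record socket-related events.

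The cost is one wording change, an optional second one, and possibly a few more expedited reports. Design, sample size and patient care are unaffected.

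### Causality is graded for SAEs only, so the non-serious skin and socket events that the ATFS could plausibly cause have no stated relatedness grade and no E-CRF item

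*Protocol*

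**What the plan says.** Section 8 defines serious and non-serious events but gives a relatedness step only to the first: the assessment of how device use relates to any SAE "will be carried out by the sponsor in collaboration with the clinical judgement of the Principal Investigator and clinic leads". The scale is limited in the same way: "reporting of SAE's will be categorised according to five different levels of causality as defined in MEDDEV 2.7/3". Events arising from socket use are left to the prosthetists to pick up and note in ordinary care, and no grading is described for them.

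Section 8 closes by saying that the risk of causally related SAEs is kept low because patients follow the standard pathway, "so procedures (design and fitting of a prosthetic socket) would still have been applied to the patients in the absence of the ATFS use". Section 6.6 describes the procedure as normal care "except that the socket will have been designed with the aid of the ATFS".

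Section 4 lists, among the hoped-for benefits of better fitting support, "reduced incidence of soft tissue problems, from irritation and sores to major injuries such as pressure ulcers". It also identifies the sponsor as the spin-out company behind the technology. Section 4.1 states that the investigation is to establish the clinical safety of the ATFS for the patients who receive the sockets.

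The E-CRF in Section 16.2 has items 1 to 12 in unbroken order. They cover IDs, dates, comfort scores, recordings, time data and the researcher's name. None concerns an adverse event or its cause. Section 10 says that study meetings monitor adverse event reporting, but it adds no grading.

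**The concern.** The ATFS recommends how to reshape the limb model into a socket. If a recommendation is poor and is accepted, the direct result is a socket that loads the limb badly. The milder consequences, irritation and sores, would not normally meet the Section 8 definition of serious, which requires death, permanent impairment, a threat to life, hospital admission or an intervention to prevent such an outcome. The events closest to the device's mode of action can therefore be recorded without anyone being asked whether the ATFS-aided design caused them.

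At stake is the reading of the safety result. At the end, the sponsor could report a number of SAEs with causality, probably very small, and an unattributed set of non-serious events, if these reach the study file at all. The closing argument of Section 8 adds a second, smaller problem: it offers reassurance about causality that does not bear on the feature the device alters.

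**Working it through.** **Step 1: what is graded.** Setting the Section 8 sentences side by side:

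| Event type | Defined | Recorded | Causality assessed | Five-level scale | E-CRF item |
|---|---|---|---|---|---|
| SAE | yes | yes | yes, sponsor with site input | yes | none |
| Non-serious socket event | yes | yes, in usual care | not stated | not stated | none |

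**Step 2: how many SAEs there may be to grade.** Inputs: 19 patients in Stage Two and at most 46 overall (Section 6.2). The protocol gives no SAE risk, so *p* is an assumption, shown over a range. Chance of at least one SAE = 1 − (1 − *p*)^n.

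| Assumed SAE risk *p* | n = 19 | n = 46 |
|---|---|---|
| 0.5% | 1 − 0.995^19 = 9% | 1 − 0.995^46 = 21% |
| 1% | 1 − 0.99^19 = 17% | 1 − 0.99^46 = 37% |
| 2% | 1 − 0.98^19 = 32% | 1 − 0.98^46 = 60% |
| 5% | 1 − 0.95^19 = 62% | 1 − 0.95^46 = 91% |

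Even at 5%, the expected number in 46 patients is only 46 × 0.05 = 2.3.

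**Step 3: how many events have no stated grade.** The rate of non-serious socket events is again assumed, from 5% to 30% of patients. Expected number = n × rate. In 46 patients this is 46 × 0.05 = 2.3 to 46 × 0.30 = 13.8. In 19 patients it is 1.0 to 5.7.

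**Step 4: share of expected events with no stated grade.** Share = non-serious rate / (non-serious rate + SAE rate); n cancels.

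- 10% and 1%: 10 / 11 = 91%.
- 30% and 0.5%: 30 / 30.5 = 98%.
- 5% and 5%, the least favourable corner of the ranges: 5 / 10 = 50%.

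Most events lack a grade whenever non-serious events are more common than serious ones.

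**Step 5: the closing argument of Section 8.** Its premise is that a socket would have been designed and fitted in any case. Section 6.6 says that the one departure from normal care is how the socket is designed. Receiving some socket is common to both pathways; the shape of the socket is not. The premise is therefore silent on whether an ATFS-aided shape caused a given harm.

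**The case against.** Several stronger readings are tempting, and the protocol does not support them.

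- *That SAEs are graded on the premise that a socket would have been fitted anyway, and so drift towards 'not related'.* The closing paragraph of Section 8 is a statement about expected risk. No rule ties an event to any level of the scale, and the stated basis for grading is clinical judgement together with the study and device documents. A lean is a possibility, not something the text sets up.
- *That the sponsor grades alone, or that one merged grade is recorded.* Assessment is "in collaboration with the clinical judgement of the Principal Investigator and clinic leads". The text does not say whether the site and sponsor views are kept separately.
- *That harms from the ATFS go ungraded altogether.* Serious socket-related harms would be graded. Section 8 itself gives an injurious fall as an example of an SAE, and an ulcer leading to admission would also qualify.
- *That a low grade could keep an SAE from the regulator.* All SAEs go to the MHRA whatever their grade, so the sponsor's interest has less consequence than it first appears.

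Two further objections carry weight. Section 4.1 says that Stage Two will verify safety and efficiency through comfort scores and design time, so the formal safety answer is not built on graded adverse events. That is so, but a comfort score does not record a skin injury or its cause, and the stated aim covers the safety of those receiving the sockets. The Clinical Investigation Plan, which the protocol cites, may also contain further adverse event rules. It is not at hand, and the point is limited to the protocol and the E-CRF it reproduces.

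Finally, the upper bounds after zero SAEs (one-sided 95%: 1 − 0.05^(1/19) = 14.6%; 1 − 0.05^(1/46) = 6.3%) reflect sample size and would be the same after any change to Section 8. They are not evidence for this point.

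**Conclusion.** The point holds in a limited form. As written, Section 8 asks about causality for SAEs only, and neither it nor the E-CRF provides a relatedness grade for non-serious socket events, although the study aims to establish clinical safety. The SAE chances in the working and the 2 to 14 ungraded events expected in 46 patients rest on assumed rates; the protocol supplies none. That most safety events would be unattributed further assumes that non-serious events outnumber serious ones. The reasoning that a socket would have been made anyway is unsound as reassurance about causality, but it is not a grading rule, and a reader should not infer biased grading from it. This is a worthwhile, cheap improvement, not a flaw that invalidates the study.

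**What to change.** In Section 8:

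1. Apply the existing five-level scale to every socket-related adverse event, serious or not.
2. Record the site Principal Investigator's grade alongside the sponsor's, and report both.
3. State that relatedness is judged against the socket shape produced with the ATFS, using the screen recordings already kept to see which recommendations were accepted or edited.
4. Remove or correct the argument that a socket would have been made anyway.

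In Section 16.2, add an E-CRF item for each adverse event and its causality grades. If the Clinical Investigation Plan already has such rules, refer to them in Section 8 and align the E-CRF.

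The cost is protocol and form wording and a few minutes per event for staff already involved. The downside is that some events will be labelled 'possible' that would otherwise carry no grade.
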